Dose, regimen, treatment cycle	
Patients will be instructed to take two 5 mg RAD001 tablets (one tablet after another) orally, with a glass of water at the same time each day in a fasting state or with a light fat-free meal.
 
RAD001 will be taken daily from Visit 2 (Day 1) until disease progression, unacceptable toxicity, or death or discontinuation from the study for any other reason.

Investigational drug	RAD001 (everolimus)
Protocol no.	CRAD001LIC01
Study phase	Phase 2
Study title	An open-label, multi-center phase 2 study to evaluate everolimus as monotherapy treatment for patients with metastatic recurrent and/or unresectable renal cell carcinoma (EVERMORE)
	Each treatment cycle is 28 days.
Supply, preparation, and administration	RAD001 will be provided by Novartis. RAD001 is formulated as tablets of 5 mg strength for oral administration. The starting dose for Cycle 1 is 10 mg/day. Tablets should be opened only at the time of administration, as the drug is both hygroscopic and light sensitive. Patients will be supplied with enough tablets for a complete 28-day cycle. Tablets should be stored in a secure, dry, light-proof medicine cabinet.
Visit schedule and assessments	Patients will present to the clinic on Day 1 and Day 15 of treatment Cycles 1, 2, and 3 and Day 1 of each subsequent treatment cycle for assessments. Please see Section 7 and Table 9 for details of assessments.
Efficacy assessment(s)	
Tumor response, SD, and progression will be assessed using the RECIST criteria. A computerized tomography (CT) scan or magnetic resonance image (MRI) of the chest/abdomen and pelvis will be obtained at screening (≤ 35 days) prior to the first dose of RAD001. Tumor response will be assessed at 8 weeks (± 1 week), and every 12 weeks (± 1 week) thereafter, until determination of disease progression (by the local radiologist) and at the end of the study. The same imaging modality used at screening must be used for all subsequent follow-up assessments.
 
Ultrasound scans cannot be used to measure tumor lesions.

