6.1.3 RAD001 Dose Level Modification/Interruption Guidelines in Case of Suspected Toxicity

Dose adjustments are permitted in those patients who are unable to tolerate the protocol-specified dosing schedule. If administration of RAD001 must be interrupted because of unacceptable toxicity, drug dosing will be interrupted or modified according to rules described in [Table 2](#), [Table 3](#), and [Table 4](#).

If the toxicity is tolerable to the patient, the initial dose should be maintained. If the toxicity is intolerable to the patient, RAD001 treatment is to be interrupted until recovery to grade ≤ 1 , then reintroduced at the initial dose or a lower dose level, depending on toxicity type and grade (see [Table 3](#)). All interruptions or dose modifications must be recorded on the Dosage Administration Record CRF.

Table 2 RAD001 Dose Level Modification Guidelines

Dose Level	Dose Schedule
0	10 mg daily
1	5 mg daily
2	5 mg every other day

Table 3 provides the procedure to be followed for dose modification and re-initiation of RAD001 in the event of toxicities suspected to be related to the study drug.

Table 3 Criteria for Dose Modification in Case of Suspected RAD001 Toxicity

Toxicity	Actions
Non-hematological toxicity	
Grade 1	No dose modification.
Grade 2 (except pneumonitis):	If the toxicity is tolerable to the patient, maintain the same dose. If toxicity is intolerable to the patient, interrupt RAD001 until recovery to grade ≤ 1 , then re-introduce RAD001 at the same dose. If the event returns to grade 2, interrupt RAD001 until recovery to grade ≤ 1 , then re-introduce at the lower dose level.
Grade 3 (except hyperlipidemia):	Interrupt RAD001 until recovery to grade ≤ 1 , then re-introduce at the lower dose level. For pneumonitis, consider the use of a short course of corticosteroids.
Grade 3 hyperlipidemia (hypercholesterolemia and/or hypertriglyceridemia):	Should be managed using standard medical therapies.
Grade 4:	Discontinue RAD001.
Reactivation of HBV or HCV	Please refer to Tables 6 and 7 .
Hematological toxicity	
Grade 1	No dose modification.
Grade 2 thrombocytopenia (platelets $<75 \times 10^9/L$, $\geq 50 \times 10^9/L$):	Interrupt RAD001 until recovery to grade ≤ 1 (platelets $\geq 75 \times 10^9/L$), then re-introduce RAD001 at the initial dose. If thrombocytopenia returns to grade 2, interrupt RAD001 until recovery to grade ≤ 1 , then re-introduce at the lower dose level.

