Grade 3 thrombocytopenia (platelets $<50 \times 10^9/L$, $\geq 25 \times 10^9/L$):	Interrupt RAD001 until recovery to grade ≤ 1 (platelets $\geq 75 \times 10^9/L$), then resume RAD001 at 1 dose level lower. If grade 3 thrombocytopenia recurs, discontinue RAD001.
Grade 4 thrombocytopenia (platelets $<25 \times 10^9/L$):	Discontinue RAD001.
Grade 3 neutropenia (neutrophils $<1 \times 10^9/L$, $\geq 0.5 \times 10^9/L$):	Interrupt RAD001 until recovery to grade ≤ 1 (neutrophils $\geq 1.5 \times 10^9/L$), then resume RAD001 at initial dose. If absolute neutrophil count (ANC) returns to grade 3, hold RAD001 until recovery to grade 1 (ANC $\geq 0.5 \times 10^9/L$), then resume RAD001 at the lower dose level. Discontinue patient from study therapy for a third episode of grade 3 neutropenia.
Grade 4 neutropenia (neutrophils $<0.5 \times 10^9/L$):	Interrupt RAD001 until recovery to grade ≤ 1 (neutrophils $\geq 1.5 \times 10^9/L$), then resume RAD001 at the lower dose level. If grade 3 or grade 4 neutropenia occurs despite this dose reduction, discontinue RAD001.
Grade 3 febrile neutropenia (not life-threatening):	Interrupt RAD001 until resolution of fever and neutropenia to grade ≤ 1 . Hold further RAD001 until the ANC $\geq 1500/mm^3$ and fever has resolved. Resume RAD001 at the lower dose level. If febrile neutropenia recurs, discontinue RAD001.
Grade 4 febrile neutropenia (life-threatening):	Discontinue RAD001.
Any hematological or non-hematological toxicity	Discontinue RAD001.

requiring interruption for ≥ 3 weeks:

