6.4 Treatment Assignment

This is a single arm study with one dose of study drug. All patients will initiate treatment with 10 mg/day RAD001.

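### Protocol Table 3 restarts RAD001 at the initial dose, not the same dose, after a first grade 2 thrombocytopenia or grade 3 neutropenia; read literally, an already reduced patient goes back to 10 mg daily

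*Protocol*

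**What the plan says.** Protocol section 6.1.3 governs dose changes for suspected RAD001 toxicity. Table 2 gives three levels: 10 mg daily (level 0), 5 mg daily (level 1) and 5 mg every other day (level 2).

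Three rows of Table 3 cover a first episode that calls for interruption and then a restart without reduction:

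- Grade 2 non-hematological toxicity that the patient cannot tolerate: "then re-introduce RAD001 at the same dose".
- Grade 2 thrombocytopenia: "then re-introduce RAD001 at the initial dose".
- Grade 3 neutropenia: "then resume RAD001 at initial dose".

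The text before the tables uses *initial* as well. For tolerable toxicity it says "If the toxicity is tolerable to the patient, the initial dose should be maintained". For intolerable toxicity the drug is interrupted, "then reintroduced at the initial dose or a lower dose level, depending on toxicity type and grade".

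The starting dose is the same for everyone. Section 6.4 states "All patients will initiate treatment with 10 mg/day RAD001", and the synopsis states "The starting dose for Cycle 1 is 10 mg/day".

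**The concern.** In a trial where every patient starts on 10 mg/day, the natural meaning of an initial dose is 10 mg/day. The protocol does not define it as the dose in use when the event began. It has no general bar on re-escalation and does not say that an earlier reduction is permanent.

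A patient can reach a lower level before a first qualifying cytopenia. Table 3 reduces the dose after grade 3 non-hematological toxicity other than hyperlipidemia, and after a recurrent grade 2 non-hematological event. The hepatitis B rules in section 6.1.4.4 also reduce it. If such a patient then has a first grade 2 thrombocytopenia or grade 3 neutropenia, the row taken at its word reverses a reduction made for a different toxicity, and does so just after a fall in blood counts.

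What is at stake is consistent and safe dosing. Section 11.9 plans 25 sites in 11 countries, and sites could read the two rows differently. One of the two readings is the less safe one.

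**Working it through.** There is no figure in the plan to reproduce. The check is a comparison of texts, the dose arithmetic, and a rough bound on numbers.

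**1. Wording side by side**

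| Situation | 6.1.3 introduction | Grade 2 non-hematological row | Two hematological rows |
|---|---|---|---|
| Tolerable toxicity | "If the toxicity is tolerable to the patient, the initial dose should be maintained" | "If the toxicity is tolerable to the patient, maintain the same dose" | no such option |
| Restart, first episode | "then reintroduced at the initial dose or a lower dose level, depending on toxicity type and grade" | "then re-introduce RAD001 at the same dose" | "then re-introduce RAD001 at the initial dose"; "then resume RAD001 at initial dose" |

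The introduction says *initial* where the non-hematological row says *same*, for the same situation. That points to *same* as the intended meaning. The two hematological rows kept the word that can be read as 10 mg.

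**2. Dose at restart (levels from Table 2)**

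| Dose at onset | Mean per day | Restart, literal reading | Ratio | Restart if *same* is meant |
|---|---|---|---|---|
| 10 mg daily | 10 mg | 10 mg daily | 10/10 = 1 | 10 mg daily |
| 5 mg daily | 5 mg | 10 mg daily | 10/5 = 2 | 5 mg daily |
| 5 mg every other day | 5/2 = 2.5 mg | 10 mg daily | 10/2.5 = 4 | 5 mg every other day |

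The readings differ only for patients already reduced.

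**3. How many patients**

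The documents give no rate for the full sequence: another toxicity, a reduction, then a first qualifying cytopenia. The following is only a guide to the order of magnitude.

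- First leg. Protocol Table 1 (section 1.2.3.3) reports suspected events of grade 3 or higher in 14 of 45 phase 1 patients on 10 mg daily: 14/45 = 0.311, exact (Clopper-Pearson) 95% CI 0.182 to 0.466. None was grade 4. Applied to the protocol's 110 patients: 110 × 0.311 = 34.2, range 110 × 0.182 = 20.0 to 110 × 0.466 = 51.3.
- Second leg. The chance p of a later first grade 2 thrombocytopenia or grade 3 neutropenia in those patients is **an assumption with no source in the documents**. Taking p as 0.01, 0.05 and 0.10, independent of the first leg: 110 × 0.311 × p = 0.34, 1.71 and 3.42 patients.
- Extremes. 110 × 0.182 × 0.01 = 0.20 and 110 × 0.466 × 0.10 = 5.13 patients.
- SAP section 3 anticipates about 142 patients. The extremes then become 142 × 0.182 × 0.01 = 0.26 and 142 × 0.466 × 0.10 = 6.62.

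The first leg overstates reductions, because grade 3 hyperlipidemia and a first grade 3 neutropenia do not lower the dose, and an interruption of 3 weeks or more means discontinuation. It understates them by leaving out recurrent grade 2 events, grade 2 pneumonitis under Table 4 and hepatitis B reactivation.

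**The case against.** The best answer is that the section itself points away from the literal reading. A dose that the patient is no longer taking cannot be maintained, so in the introduction *initial* makes sense for a reduced patient only as the dose in use. The hepatitis B rules in section 6.1.4.4 point the same way. They restart one level lower, and a patient already on the lowest dose restarts on that dose. This concerns a different toxicity, so it supports the *same dose* reading without settling it. All of this stands, and it makes a drafting slip much the likelier explanation.

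Exposure is also bounded. Restart requires recovery to grade 1 or less, and the dose never exceeds 10 mg/day. Interrupted patients are followed at least weekly (section 6.1.4), and a recurrence in either row forces a lower level. Investigators may change study drug when treating an adverse event (section 7.6.1) and must act at once where safety requires it (section 11.6). This limits harm but does not tell a site which dose is intended, and section 12 allows no authorized deviations.

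The numerical guide may also be too high. Section 1.2.3.3 says that reduced counts are frequent at the start of treatment and stay mostly within the normal range or at grade 1. Early falls make the required order of events less likely than independence implies.

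A reader might infer that the protocol deliberately plans re-escalation to full dose after a cytopenia, and might cite the mock dosing listing in the SAP (Listing 16.2-3.2), which runs 10, 5, then 10 mg. The documents do not support that. The listing is an illustrative shell, and the 6.1.3 introduction suggests the opposite intent. Nor do they support a claim that many patients would be stepped up, since no rate is given.

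**Conclusion.** The inconsistency is real, and its literal outcome is the less safe one: a 2-fold or 4-fold step-up to 10 mg daily, on recovery from a cytopenia, for a patient already reduced for another toxicity. That rests on reading the initial dose as the 10 mg/day at which all patients start. The protocol never contradicts that reading outright, although its own usage suggests that *same* was meant.

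Few patients are likely to be affected. Under the assumed second-leg rates of 1% to 10%, and if the phase 1 rate carries over, the guide gives about 0.2 to 5.1 of 110. This is not an estimate from trial data. Patients still on 10 mg are unaffected, and so are the sample size and the PFS analysis. It is a minor safety wording correction, worth making because it removes the less safe reading at almost no cost.

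**What to change.** In the grade 2 thrombocytopenia row and the grade 3 neutropenia row of Table 3, and in both places where the 6.1.3 introduction uses the term, replace the initial dose with: *the same dose (the dose being taken at onset of the event)*. A dose already reduced for another toxicity is then not raised under these rows.

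Leave Table 4 unchanged. Its grade 2 pneumonitis reduction lasts until recovery and is a separate, temporary rule.

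The cost is a few words in one section, which can go into any protocol amendment. Visits, sample size and analyses stay as they are. The change does not decide whether reductions are otherwise permanent; the protocol leaves that open.

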5.1 Inclusion Criteria

Patients may be entered in the study only if they meet all of the following criteria:

1. Age \geq 18 years old;
2. Patients with advanced renal cell carcinoma with confirmed clear or non-clear cell histology, with or without nephrectomy, and with any MSKCC prognosis;
3. Prior cytokine therapy is permitted;
4. Patients with at least one measurable lesion at baseline as per the RECIST criteria. If skin lesions are reported as target lesions, they must be documented (at baseline and at every physical exam) using color photography and a measuring device (such as a caliper) in clear focus to allow the size of the lesion(s) to be determined from the photograph;

5. Life expectancy ≥ 3 months. Life expectancy should be judged in relation to other determining patient eligibility factors such as laboratory results, Performance Status, etc.;
6. Patients with a Karnofsky Performance Status $\geq 70\%$;
7. Adequate bone marrow function as shown by: absolute neutrophil count (ANC) $\geq 1.5 \times 10^9/L$, platelets $\geq 100 \times 10^9/L$, hemoglobin (Hb) > 9 g/dL;
8. Adequate liver function: serum bilirubin ≤ 1.5 x upper limit of normal (ULN), alanine transaminase (ALT) and aspartate transaminase (AST) ≤ 2.5 x ULN. Patients with known liver metastases: AST and ALT ≤ 5 x ULN;
9. Adequate renal function: serum creatinine ≤ 1.5 x ULN;
10. Females of childbearing potential must have had a negative serum or urine pregnancy test 7 days prior to the administration of the study treatment start;
11. Patients who give a written informed consent obtained according to local guidelines.

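### Protocol Table 3 prints the restart count after a second grade 3 neutropenia as grade 1 (ANC ≥0.5 ×10⁹/L), but 0.5 is the floor of grade 3; the rest of the table points to 1.5

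*Protocol*

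**What the plan says.** Table 3 sets the dose changes for suspected RAD001 toxicity. Its grade 3 neutropenia row opens with the definition "Grade 3 neutropenia (neutrophils $<1 \times 10^9/L$, $\geq 0.5 \times 10^9/L". It then gives three steps:

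- First episode: interrupt until grade ≤1, with the count spelled out as "neutrophils $\geq 1.5 \times 10^9/L$), then resume RAD001 at initial dose".
- Return to grade 3: "hold RAD001 until recovery to grade 1 (ANC $\geq 0.5 \times 10^9/L", then resume at the lower dose level.
- Third episode: stop study therapy.

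The other neutropenia rows that allow a restart also give a count. For grade 4 neutropenia, recovery to grade ≤1 is "neutrophils $\geq 1.5 \times 10^9/L$), then resume RAD001 at the lower dose level". For grade 3 febrile neutropenia the rule is "Hold further RAD001 until the ANC $\geq 1500/mm^3$ and fever has resolved". The two platelet rows that allow a restart give "platelets $\geq 75 \times 10^9/L$), then re-introduce RAD001 at the initial dose" (grade 2) and "platelets $\geq 75 \times 10^9/L$), then resume RAD001 at 1 dose level lower" (grade 3), each time as the count for grade ≤1. Inclusion criterion 7 in Section 5.1 asks for "absolute neutrophil count (ANC) $\geq 1.5 \times 10^9/L".

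SAP Section 3.2 refers back to Protocol Tables 2, 3 and 4 for dosing rules and gives no counts of its own.

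**The concern.** The second-episode instruction joins a grade and a count that describe different patients. A site that reads the grade waits until neutrophils reach 1.5. A site that reads the count could restart at 0.6, with the patient still in the grade that triggered the hold. The printed number also sets a lower bar after the second episode than after the first, the reverse of what a graded toxicity rule is for.

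There is a knock-on effect. The stop rule counts episodes. A patient restarted between 0.5 and 1.0 has not left grade 3, so it is unclear when a third episode begins.

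Table 3 is the operative dosing rule, and Protocol Section 12 allows no authorised deviations. Section 1.2.3.3 says that some patients may be particularly sensitive to myelosuppression.

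**Working it through.** No sample-size or power figure is involved. The check is a comparison of thresholds, with one unit conversion.

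**Step 1. Conversion.** 1500/mm³ = 1500 × 10⁶/L = 1.5 × 10⁹/L.

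**Step 2. Every numeric haematological restart limit in Table 3, side by side (×10⁹/L).**

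| Row | Label for recovery | Printed limit | Equals the table's own grade ≤1 value? |
|---|---|---|---|
| Grade 2 thrombocytopenia | grade ≤1 | 75 | yes |
| Grade 3 thrombocytopenia | grade ≤1 | 75 | yes |
| Grade 3 neutropenia, first episode | grade ≤1 | 1.5 | yes |
| Grade 3 neutropenia, second episode | grade 1 | 0.5 | **no** |
| Grade 4 neutropenia | grade ≤1 | 1.5 | yes |
| Grade 3 febrile neutropenia | grade ≤1 | 1.5 | yes |

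Five of the six limits match the grade in their label, as do three of the four for neutrophils. The entry limit is also 1.5.

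**Step 3. Test the printed limit against the row's own definition.** Grade 3 means 0.5 ≤ ANC < 1.0. The restart condition as a number is ANC ≥ 0.5. Every value in the grade 3 range meets it, so on the number alone the hold would have no length. The number is also the boundary between grade 3 and grade 4. Its ratio to the table's grade ≤1 limit is 0.5/1.5 = 1/3.

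**Step 4. Where the two readings differ.** They disagree for ANC from 0.5 to below 1.5. The safety-relevant part is 0.5 to below 1.0, which is grade 3. From 1.0 to below 1.5, Table 3 has no row that requires interruption, so a restart there matters little.

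**Step 5. Look for a passage that settles the count.** Sections 6.1.3, 6.1.4, 6.6.3.1 and 7.6.5.1 speak of recovery to grade ≤1, grade 1 or baseline. They support the label, but none gives a neutrophil count for this step. Section 1.3 lists a change to Table 3 among the amendments; the entry examined here is in the current table.

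**The case against.** Four points can fairly be made on the other side.

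*It may be an extraction error.* The case rests on one digit in text read from a PDF, and nearby text shows damage: one cell of the hepatitis B action table appears to have lost a symbol, and a Table 9 footnote carries the wrong letter. A 1.5 misread as 0.5 cannot be ruled out from this text. This stands, and it is why the fix begins with the source document.

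*The row largely corrects itself.* A count of 0.5 to below 1.0 is not grade 1 under the row's own definition, and the preceding instruction gives grade ≤1 as 1.5. A careful reader would wait. This stands as a reason to think harm unlikely, but it leaves a wrong threshold in a dosing table.

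*There are safeguards.* Patients whose drug is interrupted are followed at least weekly (Sections 6.1.4 and 6.6.3.1). Blood counts are repeated until baseline or grade 1 (Section 7.6.5.1). The restart is at a lower dose, and a third episode ends treatment. Section 11.6 expects investigators to act for a patient's safety even when that departs from the protocol. All of this reduces the risk. None of it bars a restart at 0.5.

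*The event is probably rare.* Section 1.2.3.3 says reduced counts mostly stayed normal or grade 1, and reports grade 3 neutropenia as a dose-limiting toxicity in one patient. If the denominator is the 147 single-agent patients (an assumption), that is 1/147 = 0.7%. This would be 110 × 1/147 = 0.75 patients at the protocol's planned size, or 142 × 1/147 = 0.97 at the SAP's. It is not a rate for all grade 3 episodes, and the disputed number applies only at a second one. Section 6.1.2 does list neutropenia among the most frequent laboratory abnormalities, though most adverse events were grade 1 to 2. The point about rarity stands, but gives no usable estimate.

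A reader might go further and infer that the plan deliberately permits dosing through grade 3 neutropenia, or that patients were exposed to it. The documents support neither. The words require grade 1, every comparable limit is 1.5, no rationale for a looser second bar is given, and nothing shows how sites applied the row.

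**Conclusion.** The point holds as an internal contradiction in one dosing threshold. As printed, the number is the floor of grade 3, one third of the limit used everywhere else for neutrophils, and incompatible with its own label. The intended value is almost certainly 1.5 ×10⁹/L. That conclusion rests on the consistency of the other five limits and the entry criterion, and on the extracted digit being what the source document shows.

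It is worth correcting because it governs redosing, nothing else in the documents supplies the right count for this step, and the repair is nearly free. The likely harm is small, and the number of patients affected is not estimable. It should not be read as a weakness of the efficacy evidence: the limit enters neither the sample-size calculation nor the definition, censoring or Kaplan-Meier estimation of PFS.

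**What to change.** First check the source document. If it shows 1.5, no change is needed. If it shows 0.5, amend the second-episode step of the grade 3 neutropenia row to read grade ≤1 (ANC ≥1.5 ×10⁹/L), by written amendment under Protocol Section 11.6.

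The cost is a slightly longer hold for the few patients who would otherwise have restarted between 0.5 and 1.5. Some of them might reach the Table 3 rule that ends treatment after an interruption of 3 weeks or more. Sample size and analysis do not change.

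If dosing has already ended, the amendment serves no purpose. (The planned last visit was 30 January 2012, and the SAP pages are dated September 2017.) The useful step is then to set the dosing records (SAP Listing 16.2-3.2) against the dated neutrophil counts (Listing 16.3-1.1) and report any restart below 1.5 after a second grade 3 episode. Both listings are already planned.
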